Vendor/Collaborator	Adelphi Real World Ltd	
Rationale	This study will provide data on patient characteristics and treatment patterns of HIV positive patients initiating raltegravir 1200mg once daily (RAL OD) (2 x 600mg). There is a lack of published real world data on the use of once daily raltegravir, and these data will show how RAL OD is used in the real world setting in the UK.	
Primary Objective	To describe and understand the real world utilisation of RAL OD.	
Primary Outcome measures	Description of patient demographics (age, gender, and ethnicity), baseline clinical and treatment characteristics (co-morbidities, co-medications, AIDS defining illnesses within the last 6 months/ever) in ART naïve and experienced HIV-1 infected adult subjects. Description of Antiretroviral therapy (ART) treatment combination initiated with RAL OD. If treatment experienced, description of prior ART regimen. Description of clinical and treatment characteristics (co-morbidities, co-medications) of subjects who remain on RAL OD at the 6 month time point. Description of any change in clinical and treatment characteristics from baseline to 6 months in subjects who	
Secondary Data Collection Objective	remain on treatment Laboratory parameters at baseline and 6 months (HIV viral load, CD4 cell count), RAL OD discontinuations at 6 months	
Study Design	Non-interventional, observational, multi-centre, retrospective chart review study	
Study Population	HIV-1 infected adults initiating RAL OD as part of their ART at treatment centres within the UK from September 2017	
Study Duration	The study duration is expected to be 6-12 months. Patient data will be collected on all patients starting RAL OD from September 2017 who return for their 6 month (-1/+3 months window) follow up appointment. Eligible patients	

Protocol/Amendment No.: RETRO STUDY, v0.3

VEAP ID NO: 7651

	must have completed their 6 month follow up before 31st		
	December 2018		
Exposure and Outcome	Exposure: RAL OD based ART		
	Outcomes: descriptive utilisation and treatment patterns.		
	Clinical measures (HIV viral load and CD4 cell counts)		
	will be captured as secondary endpoints.		
Statistical Methods	The profile of HIV-1 positive subjects initiating treatment		
	with RAL OD will be analysed descriptively using		
	summary statistics.		
Sample Size and Power	Sample size of 300 across 2 centres. This is large enough		
Calculations	to provide precise estimates overall and allow sub-group		
	assessments. This will be a descriptive analysis - power		
	calculations are therefore not applicable.		
Limitations	Retrospective Database Analysis carries the potential for		
	missing data.		
	Non-randomised: Sampling limited to sequential		
	systematic sampling due to treatment being newly		
	available		

1 **Background and Rationale**

1.1 Background

Highly active antiretroviral therapy (ART) has changed human immunodeficiency virus (HIV) infection from a fatal illness to a manageable chronic disease. Current British HIV Association (BHIVA) treatment guidelines for HIV infection recommend therapy naïve people living with HIV (PLWH) start ART containing two nucleoside reverse transcriptase inhibitors (NRTIs) plus one of the following: ritonavir boosted protease inhibitor (PI/r), non-nucleoside reverse transcriptase inhibitor (NNRTI) or integrase strand transfer inhibitors (INSTI) (1). The INSTI class is the most recent class of drugs to be developed for HIV therapy. This group of medications appears to cause a more rapid decline in viral load when compared to PI or efavirenz (EFV) containing regimens. (2)

Raltegravir, 400 mg tablets twice daily (RAL BID), was the first agent of INSTI class approved for clinical use by the FDA in 2007(3). Multiple trials demonstrated RAL BID to be a very effective agent in both treatment-naïve and -experienced patients when used with either tenofovir disoproxil fumarate (TDF)/emtricitabine (FTC) (4, 5) or abacavir (ABC)/lamivudine (3TC) (11, 12). RAL has demonstrated rapid HIV viral suppression and is considered to be a well-tolerated antiretroviral medication with few drug interactions, no food requirement, and a well-documented adverse effect profile in both treatment-naïve and -experienced, HIV-infected patients (2, 6). Due to lack of significant drug-drug interactions, RAL is a preferred option for patients on multiple medications (7).

Protocol/Amendment No.: RETRO STUDY, v0.3

VEAP ID NO: 7651

RAL BID has the longest post-marketing experience of the INSTI class; both clinical trials and clinical experience have demonstrated durable virologic suppression in treatment-naïve and treatment-experienced patients, including patients with extensive antiretroviral experience and documented antiretroviral resistance. (7) A new 1200 mg, once-daily formulation of RAL (RAL OD), administered orally as two 600 mg tablets, was found to have non-inferior efficacy compared to RAL BID in a randomised clinical trial of treatment naïve HIV-1 infected patients (ONCEMRK).(8) RAL OD gained Marketing Authorization in July 2017 and was first available for prescription in September 2017. Once-daily regimens are often preferred by both patients and clinicians in order to facilitate adherence and improve patient quality of life. The RAL OD formulation administers a higher daily dose of raltegravir, as compared to RAL BID, in order to sustain sufficient trough concentrations (8).

1.2 Rationale

The ONCEMRK trial (8) evaluated RAL OD in treatment naïve HIV-1 infected patients. The extensive clinical experience with RAL BID will likely translate to the RAL OD formulation and influence the use of this new formulation. As RAL OD becomes more widely available for prescription, understanding the patient population in which it is preferentially prescribed (i.e. the patients' demographic and clinical profiles) as well as its overall effectiveness in clinical practice, may facilitate further insight as to its clinical impact in both ART naïve and experienced patients, including those switched from RAL BID, in the real world setting

Objectives and Hypotheses

2.1 Primary Objectives & Hypothesis

This study is purely descriptive, and as such no formal hypothesis will be tested. It will explore how and to whom RAL OD is being prescribed in the UK outside of the clinical trial setting. Specific primary objectives are as follows:

- To describe demographic (age, gender, ethnicity), baseline clinical and treatment characteristics (co-morbidities, co-medications) in ART naïve and experienced HIV-1 infected adult subjects who have been initiated on RAL OD.
- To describe Antiretroviral Therapy (ART) treatment combination initiated with RAL OD.
- To describe prior ART regimen in treatment experienced subjects.

2.2 Secondary Objectives

Protocol/Amendment No.: RETRO STUDY, v0.3

VEAP ID NO: 7651

The secondary study objectives are as follows:

• To describe clinical and treatment characteristics at 6 month (co-morbidities, co-medications) in subjects who have been initiated as above, and have data available at 6 month (-1/+3 months) follow up appointment, specifically:

1. To describe:

- Proportion of subjects still taking RAL OD
- Proportion of patients with virologic suppression (<50 copies/ml) in ART naïve patients
- Proportion of patients who maintain virologic suppression (<50 copies/mL) at follow up visit in ART experienced patients
- Viral load in ART naïve patients.
- Viral load in ART experienced patients
- Percent and absolute change in CD4 cell count from RAL OD initiation
- Proportion of patients with RAL OD discontinuation
- 2. To describe characteristics of subsequent ARV regimens among patients who are switched from RAL OD based regimens to other ARV regimens.
- 3. To describe change in clinical and treatment characteristics of patients who remain on RAL OD for the study time period.

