3 METHODOLOGY

3.1 Summary of Study Design

This is a non-interventional, retrospective observational chart review study at 2 UK treatment centres that will utilize electronic data capture (EDC) to address study objectives.

The study will capture data from 300 HIV-1 positive adult subjects receiving RAL OD as part of their ART at UK NHS treatment centres. NHS records generally capture all of the usual care of an HIV positive patient including their physical exams, diagnoses, laboratory findings, medication prescriptions, co-morbidities, social history and demographic data.

All eligible HIV-1 infected adult patients (\geq 18 years) who initiated RAL OD based ART from September 2017 will be included in this study on a sequential sampling basis. Data from eligible patients' medical charts will be extracted for the time of initiation and at 6 months (window of -1/+3 months) post-initiation follow up appointment.

The index ARV regimen is defined as the first RAL 1200mg OD (2 x 600mg) containing ARV regimen a patient receives and the baseline will be defined as the RAL 1200mg OD

Protocol/Amendment No.: RETRO STUDY, v0.3

VEAP ID NO: 7651

initiation prescription date. Treatment with RAL OD must have been initiated during or after September 2017 and before April 1st 2018 for the primary baseline data collection. Subjects should have at least one 6 month (-1/+3 months) follow up appointment before December 31st 2018 to ensure 6 month secondary outcomes data are available for analysis. Chart review will only be carried out once a patient has completed the 6 month visit to ensure all data are captured retrospectively.

This time period was selected based on expectations of RAL OD utilization over time in the post-launch period and standard UK practice of 6-monthly clinic appointments.

The final analysis will be conducted following database lock after the last study participant has reached the 6 (-1/+3) months treatment milestone, by December 31st^h 2018, and all data queries have been resolved.

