4.1 Exposure

Subjects treated with RAL OD will be identified by the administering clinicians within the treatment centres. Unless they discontinue treatment during the study period, subjects will have been taking RAL OD for at least 6 months.

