8.1.2 Secondary objectives

a) Clinical and treatment characteristics (co-morbidities, co-medications, ART, discontinuations)

Clinical and treatment characteristics and changes from baseline in all subjects who have data available at the follow up appointment will be analysed descriptively using summary statistics. These will include the mean, median, standard deviation, and 95% confidence interval of the mean for continuous variables and frequency distributions for categorical variables.

b) Virologic and immunologic outcomes

Virologic and immunologic outcomes will be analysed descriptively at baseline and follow up appointment. Test results closest to the 6 month time point will be used for these analyses.

Frequency and proportion of patients with virologic suppression (Section 3.1) at baseline and 6 months will be described.

Among the virologically suppressed patients at baseline, frequency and proportion of patients with sustained virologic suppression, and viral load measures (Section 3.1) at 6

Protocol/Amendment No.: RETRO STUDY, v0.3

VEAP ID NO: 7651

months will be described. Data will be presented as the mean, median, interval of the mean for continuous variables and frequency distributions for categorical variables. A mean change from RAL OD initiation in CD4 cell count will be described at the 6 month time point.

Per Protocol Analysis: Primary Objective = All subjects who initiated RAL OD treatment.

Secondary Objective: Numerator = patients who remained on RAL OD treatment for the 6 month study period; Denominator = all patients who initiated RAL OD therapy.

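### Persistence and discontinuation are reported as 6-month results, but treatment status is read at an appointment that may fall anywhere from month 5 to month 9

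*Protocol*

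**What the plan says.** The protocol uses two time anchors for the same secondary outcome.

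**The appointment.** Section 2.2 applies to subjects who "have data available at 6 month (-1/+3 months) follow up appointment" and lists "Proportion of subjects still taking RAL OD" and the proportion discontinuing among the items to be described. Section 3.1 says that chart data "will be extracted for the time of initiation and at 6 months (window of -1/+3 months) post-initiation follow up appointment", and that "Chart review will only be carried out once a patient has completed the 6 month visit". An appointment at month 5 or at month 9 satisfies these statements equally.

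**Six months.** The synopsis names "RAL OD discontinuations at 6 months" as a secondary item. Section 8.1.2 gives, for the secondary objective, "Numerator = patients who remained on RAL OD treatment for the 6 month study period", over a denominator of all initiators. Section 4.1 states that, discontinuers apart, "subjects will have been taking RAL OD for at least 6 months".

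One rule does tie data to month 6. Section 8.1.2(b) selects the test result nearest that time. It stands under virologic and immunologic outcomes and does not extend to treatment status. Section 4.3 lists the RAL OD initiation date; it lists no stop, switch or last-known-on-treatment date.

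**The concern.** A visit window is normal in a chart review and is a sensible way to select laboratory values. The difficulty is using the same window to decide whether a patient is still on treatment while labelling the answer as a 6-month result. The proportion discontinued can only rise with time since initiation, so a crude proportion read at visits between month 5 and month 9 depends partly on when patients were seen. It also pools exposure times that can differ by a factor of 9/5 = 1.8.

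At stake are the secondary persistence and discontinuation proportions. Two analysts working from this protocol could classify the same patient differently, and the published 6-month figure could not readily be compared with a figure from a study that fixes the time point. The primary objectives (who receives RAL OD, and in what regimen) are not affected.

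**Working it through.** **1. Two patients against the text**

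| Patient | Status at the appointment (2.2, 3.1) | Six months on treatment (synopsis, 4.1, 8.1.2) |
|---|---|---|
| Seen on RAL OD at month 5 | Persistent | Not established by that visit |
| Stops at month 7, seen at month 8 | Discontinued | Persistent if the 6-month study period is a fixed 6 months; discontinued if it runs to the visit |

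The protocol gives no rule for either patient.

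**2. Size: inputs**

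- Window: 6 − 1 = 5 months to 6 + 3 = 9 months (sections 2.2 and 3.1).
- Sample size: 300 (section 3.1).
- Discontinuation rate: not in the protocol, so there is no figure of its own to reproduce. Assumed cumulative discontinuation by month 6: p = 5%, 10%, 20% or 30%.

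**3. Constant hazard**

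F(t) = 1 − (1 − p)^(t/6). For p = 10%:

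- month 5: 1 − 0.9^(5/6) = 8.4%
- month 6: 10.0%
- month 9: 1 − 0.9^(9/6) = 14.6%

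| Assumed p at month 6 | All seen at month 5 | All seen at month 9 | Gap (points) | 95% half-width, n = 300 (points) |
|---|---|---|---|---|
| 5% | 4.2% | 7.4% | 3.2 | 2.5 |
| 10% | 8.4% | 14.6% | 6.2 | 3.4 |
| 20% | 17.0% | 28.4% | 11.5 | 4.5 |
| 30% | 25.7% | 41.4% | 15.7 | 5.2 |

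The half-width is 1.96 × √(p(1 − p)/300); gaps are taken before rounding. At p = 10%, reading everyone at month 5 misses about 300 × (0.1000 − 0.0841) ≈ 5 stops that occur by month 6. Reading everyone at month 9 adds about 300 × (0.1462 − 0.1000) ≈ 14 that occur after it.

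**4. Less extreme cases, p = 10%**

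- Visits uniform over months 5 to 9: with λ = −ln(0.9)/6 = 0.01756 per month, the mean of F is 1 − (e^(−5λ) − e^(−9λ))/(4λ) = 1 − (0.9159 − 0.8538)/0.07024 ≈ 11.5%. That is about 1.5 points above 10% and within the 3.4-point half-width.
- Front-loaded stopping (Weibull, shape 0.5): F(t) = 1 − (1 − p)^√(t/6) gives 9.2% at month 5 and 12.1% at month 9.

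**The case against.** The strongest reply is that the protocol uses 6 months as a windowed term. Section 3.1 attaches the −1/+3 months to the treatment milestone itself, so the study period in section 8.1.2 can be read as ending at the windowed visit. On that reading the month-7 stopper seen at month 8 is a non-persister under both sections. This stands, and for that reason a reader who infers a flat contradiction between sections 2.2 and 8.1.2 goes too far: what is established is an ambiguity. It does not rescue section 4.1, whose minimum of 6 months a month-5 visit cannot demonstrate.

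Second, the month-5 and month-9 readings are the edges of the window. Section 3.1 refers to 6-monthly appointments as standard practice, so visits should cluster nearer month 6. This stands too; the edge figures are bounds, not an expected bias.

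Third, a reader might infer that the result will differ between centres or patient groups because of their visit schedules. The protocol does not show that schedules differ, and it plans a purely descriptive analysis. Such differences are possible, not certain.

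Fourth, section 4.3 is headed as covariates and also omits discontinuation status and the subsequent regimen, which the objectives require. It is therefore not a complete list of fields, and the absence of a stop date there does not prove that none will be collected. Section 3.1 says NHS records generally hold prescriptions, and section 3.2 requires initiation at least 6 months earlier, so month-6 status should often be recoverable. This weakens the claim that the data will be missing, but it also shows that the remedy is feasible. A separate SAP could choose a classification rule; it could not supply dates that were never extracted.

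Finally, one might want a Kaplan-Meier curve from all initiators. The protocol does not support that: inclusion depends on a completed follow-up visit, so the sample is already selected on having returned, and few patients would be censored early.

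**Conclusion.** The point holds in a limited form. The secondary persistence and discontinuation proportions carry a 6-month label, but status is taken at an appointment between months 5 and 9. A visit before month 6 cannot establish 6 months on treatment, and the classification of stops between months 6 and 9 depends on which reading of the study period is adopted.

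The size rests wholly on assumed discontinuation rates. At an assumed 10% by month 6 with constant hazard, the bounds are 8.4% and 14.6%, and evenly spread visits give about 11.5%; front-loaded stopping narrows the bounds to 9.2% and 12.1%. A realistic bias is modest and may lie within sampling error at n = 300. The correction is still worth making, because the outcome should have one definition and the change is cheap.

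**What to change.** - Collect the RAL OD stop or switch date and the last date known on treatment.
- Define persistence and discontinuation as status at a fixed 6 months (for example day 183), reported as a proportion with a 95% CI. Use Kaplan-Meier only where patients are last known on treatment before that day.
- Keep the −1/+3-month window for laboratory values and the other visit-based characteristics (co-morbidities, co-medications), which still need a time rule.
- Reconcile sections 2.2, 4.1 and 8.1.2 to this definition.
- State that the estimate applies to patients who met the follow-up-visit requirement. This change does not remove that selection.

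The cost is one or two date fields in the data collection tool and a short edit to three sections. Some stop dates will be approximate.

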3 METHODOLOGY

3.1 Summary of Study Design

This is a non-interventional, retrospective observational chart review study at 2 UK treatment centres that will utilize electronic data capture (EDC) to address study objectives.

The study will capture data from 300 HIV-1 positive adult subjects receiving RAL OD as part of their ART at UK NHS treatment centres. NHS records generally capture all of the usual care of an HIV positive patient including their physical exams, diagnoses, laboratory findings, medication prescriptions, co-morbidities, social history and demographic data.

All eligible HIV-1 infected adult patients (\geq 18 years) who initiated RAL OD based ART from September 2017 will be included in this study on a sequential sampling basis. Data from eligible patients' medical charts will be extracted for the time of initiation and at 6 months (window of -1/+3 months) post-initiation follow up appointment.

The index ARV regimen is defined as the first RAL 1200mg OD (2 x 600mg) containing ARV regimen a patient receives and the baseline will be defined as the RAL 1200mg OD

Protocol/Amendment No.: RETRO STUDY, v0.3

VEAP ID NO: 7651

initiation prescription date. Treatment with RAL OD must have been initiated during or after September 2017 and before April 1st 2018 for the primary baseline data collection. Subjects should have at least one 6 month (-1/+3 months) follow up appointment before December 31st 2018 to ensure 6 month secondary outcomes data are available for analysis. Chart review will only be carried out once a patient has completed the 6 month visit to ensure all data are captured retrospectively.

This time period was selected based on expectations of RAL OD utilization over time in the post-launch period and standard UK practice of 6-monthly clinic appointments.

The final analysis will be conducted following database lock after the last study participant has reached the 6 (-1/+3) months treatment milestone, by December 31st^h 2018, and all data queries have been resolved.

3.2 Study Population

The study will be conducted in 2 NHS hospital HIV departments in the UK. To ensure the data are representative of the UK, centres will be chosen to represent London and non-London in proportion with the treated patient population. As approximately 50% of UK HIV patients are treated in London, one of the potential sites will be selected from the largest treatment centres in London. The additional site will be a non-London treatment centre, and will be selected primarily based on the number of eligible patients treated.

Patients who were initiated on RAL OD at least 6 months ago will be identified by the clinician, Principal Investigator or a member of the clinical team, from review of hospital records and databases as appropriate at each centre. From a list of eligible patients with the required data, the earliest recent record will be recorded as the first participant and then all further eligible participants up to 150 per centre will be selected sequentially to minimize bias.

It is intended that approximately 150 patients will be included from each participating centre to represent a proportionate spread. Oversampling may be performed in the larger centre in order to maintain an overall sample size of 300.

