3.3 Inclusion Criteria

HIV-1 infected patients initiating RAL OD based ART during or after September 2017 and before April 30th 2018 will be included in the study sample if they meet the following inclusion criteria:

- 1) A diagnosis of HIV-1 infection
- 2) At least 18 years of age at the index date

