8.2 Bias

It is intended that data will be collected on consecutive patients in who at least 6 months follow-up was possible (i.e. started RAL OD during or after September 2017). Eligible patients must have completed their 6 month follow up before 31st December 2018. This will include any patients who may have moved treatment centres since initiation. Participating centres will be selected to be representative of the UK population, one site from within London (where approximately 50% of HIV patients in the UK are currently treated) and one from outside London will be used.

The study is a retrospective chart review study that will be using data extracted from databases; any missing data will be queried with the sites and if not available, will be recorded as such.

Any observational study has the possibility of residual confounding due to unknown risk factors [13]. However this study is designed to collect information on recent prescribing practice and is based on clinical experience and knowledge of the HIV physician.

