8.2.1 Methods to Minimize Bias

By including 2 treatment centres we hope to reduce single centre bias. Furthermore, to minimise bias and to ensure a sample population which is representative of UK, site selection will be based on treatment hubs within areas of high prevalence.

As approximately 50% of UK HIV patients are treated in London one of these treatment centres will be randomly selected from the 6 largest treatment centres in London. The other treatment centre will be a non-London centre.

Patients who from September 2017 were initiated on RAL OD for at least 6 months and who completed their 6 month follow up before 31st December 2018, up to 150 patients per site initially, will be selected sequentially to minimise bias. Should the larger site continue to recruit additional patients in order to meet the target of 300, the same methods will be used.

Protocol/Amendment No.: RETRO STUDY, v0.3

VEAP ID NO: 7651

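### Two centres, one of them picked mainly on its number of RAL OD starters, cannot support the claim that the data represent UK practice

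*Protocol*

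**What the plan says.** The target is national. Section 2.1 says of the study: "It will explore how and to whom RAL OD is being prescribed in the UK outside of the clinical trial setting".

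The protocol claims three times that site selection delivers this. Section 3.2: "To ensure the data are representative of the UK, centres will be chosen to represent London and non-London in proportion with the treated patient population". Section 8.2: "Participating centres will be selected to be representative of the UK population". Section 8.2.1 repeats the aim of a UK-representative sample.

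The two sites are chosen by different rules:

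- **London**, section 8.2.1: "one of these treatment centres will be randomly selected from the 6 largest treatment centres in London".
- **Non-London**, section 3.2: "The additional site will be a non-London treatment centre, and will be selected primarily based on the number of eligible patients treated". Section 8.2.1 adds no such criterion and says only: "The other treatment centre will be a non-London centre". The same section describes site selection in general as resting on treatment hubs where prevalence is high.

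Section 3.3 settles who counts as eligible: "HIV-1 infected patients initiating RAL OD based ART during or after September 2017 and before April 30th 2018 will be included in the study sample".

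Section 3.2 plans about 150 patients per centre and allows the larger centre to be oversampled to keep the total at 300. The limitations in the synopsis and in section 8.2.3 cover missing data, sequential sampling, validity of chart data and transcription error. Neither mentions selection on RAL OD volume or generalising from two centres.

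**The concern.** The number of RAL OD starters at a clinic depends on how many HIV patients it treats and on how readily its clinicians prescribe the drug. A clinic can rank high because it is large, or because it has a local practice, for instance moving established patients across. In the second case the same practice shapes what the primary objectives describe: prior ART regimen, the accompanying ART, and the balance of naïve and experienced patients.

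With one clinic per region, the reader of the results cannot tell regional practice from clinic policy. Sequential sampling within the clinic does not help, because it acts below the level at which the selection happened. The results are meant for conferences and a journal, so a description of two clinics could be published as a description of the UK.

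**Working it through.** **1. The plan's own figure.** 2 centres × 150 patients = 300. This agrees with the stated sample size. The protocol gives no precision target, so there is no other figure to reproduce.

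**2. What the selection count measures.** Section 3.3 defines the sample as patients starting RAL OD in the window, and the next paragraph of 3.2 builds the list of eligible patients from those started on it. So the count in 3.2 is a count of starters, not of HIV caseload:

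starters = clinic caseload × local propensity to start RAL OD.

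Only the second factor can distort the description, and it does so only if it differs between centres.

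**3. What two centres can show.** There are 2 centres in 2 regions, so 2 − 2 = 0 degrees of freedom remain for variation between centres within a region. The data cannot show how far either clinic is typical of its region.

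**4. How a gap at one centre carries into the pooled result.** Let *w* be that centre's share of the sample and *d* the gap, in percentage points, between the centre and its region. The pooled figure moves by *w* × *d*. The protocol does not give *d*, so the values below are assumptions.

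| *d* (assumed) | 150 of 300, *w* = 0.5 | 200 of 300 after oversampling (assumed), *w* = 0.67 |
|---|---|---|
| 0 | 0 | 0 |
| 5 | 2.5 | 3.3 |
| 10 | 5.0 | 6.7 |
| 20 | 10.0 | 13.3 |

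For scale, 300 independent patients and a percentage near 50 give a 95% half-width of 1.96 × √(0.25/300) = 5.7 points. The protocol does not state this figure. It does not include any shift of the kind in the table.

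**5. Whether choosing on starter count tends to create a gap.** A simulation took 10 or 30 candidate centres and let the propensity to switch patients vary between them (log-SD 0, 0.3 or 0.6), with clinic size varying by log-SD 0 or 0.5. All of these are assumptions.

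- With log-SD 0 for propensity, the centre with the most starters shows no gap.
- With 0.3 to 0.6, switchers make up 53% to 77% of starters at that centre, against 51% to 54% across all candidates. The smallest gap is 53.4 − 51.0 = 2.4 points and the largest 76.9 − 54.3 = 22.6, or 1.2 to 11.3 points in the pooled result at *w* = 0.5.
- Variation in clinic size shrinks the gap, because the count then reflects size more than propensity.

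This shows the direction under one model. It does not estimate the effect in this study.

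**6. Ordinary clustering.** Even without selection on volume, patients in one clinic resemble each other. For an assumed intraclass correlation of 0.01 to 0.10, the design effect 1 + 149 × ICC is 2.49 to 15.9. The effective sample size is then about 120 down to 19, and the half-width for a statement beyond the two clinics is 8.9 to 22.6 points.

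**The case against.** The strongest reply has four parts.

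- **Volume is a feasibility condition.** About 150 starters are needed at each centre within seven or eight months of first availability, and section 8.3 says that the sample size depends on uptake. This stands. Wanting a high-volume site is reasonable.
- **A high-volume centre holds more of the target population.** The study concerns RAL OD starters, not all HIV patients, so a rule based on total caseload is not clearly better. This also stands, and it is why the selection rule itself need not be overturned.
- **The split by region already addresses representativeness.** It does so for geography only, in proportion to all treated HIV patients rather than RAL OD starters, and the permitted oversampling can undo it.
- **Section 8.2.1 is modest in places.** It speaks of hoping to reduce single-centre bias. But it then states UK representativeness as an aim that site selection secures, and the limitations do not take it back.

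A reader might go further and infer that the site is selected on the study's outcome. The documents do not support that. No uptake rate is estimated, non-users are not sampled, and the primary objectives describe only patients who started. Nor does section 3.2 say that the centre with the most starters must be taken; the count is the main criterion, not the only one. By-centre tables may also already be planned in a SAP not shown, so their absence from the protocol is not a fault.

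**Conclusion.** The concern holds as a claim that the design cannot support. One clinic per region, with the non-London one chosen mainly on its number of RAL OD starters and with oversampling allowed, does not ensure data representative of UK prescribing. The stated limitations do not say so, and sections 3.2 and 8.2.1 do not give the same rule for the non-London site.

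The size is unknown. The shift is *w* × *d*, and the protocol does not give *d*. The part due to selecting on starter count is zero if prescribing propensity does not vary between centres. The inability to generalise from one centre per region remains in either case.

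Two stronger conclusions are tempting. One is to put a definite figure on the bias by assuming a wide spread between centres with the chosen one at the extreme; the documents give neither the spread nor the centre's place in it. The other is to require that the non-London site be redrawn at random by caseload. That is a debatable trade-off, since it would still need a minimum number of starters and could miss the target of 300.

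**What to change.** 1. In sections 3.2, 8.2 and 8.2.1, replace the statement of UK representativeness with a description of practice at two large centres, one in London and one outside, and limit the conclusions to them.
2. In section 8.2.3, add that the non-London centre was selected on RAL OD volume, and that one centre per region gives limited generalisability.
3. Present the primary tables by centre as well as pooled, so that a clinic-specific pattern and any imbalance from oversampling can be seen.
4. State one selection rule for the non-London centre, reconciling the number of eligible patients (3.2) with the high-prevalence hubs (8.2.1).

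The cost is protocol wording, an extra table column and a more modest claim. No further data are needed and the sites need not change.
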